8. RESEARCH METHODS

8.1. Study design

This is a multi-center post-marketing observational study. It has been defined according to the NUTS (Nomenclature of Territorial Units for Statistics: Nomenclature d'unités Territoriales Statistiques, French) criteria, which is a regional classification, created in order to reduce interregional disparities in socio-economic analysis of the regions, and to produce data comparable to that of the European Union (EU). Turkey has been divided into 12 NUTS regions depending on the economic, social, cultural, and geographical aspects, and the population size. In this study, patients with metastatic renal cell carcinoma from centers in 12 NUTS regions of Turkey will be included, who meet the inclusion criteria. Since this is a non-interventional observational study, there is no specific follow-up protocol. In this study, approximately 152 patients planned to be recruited in a year and followed-up 12 months.

This is a multi-center post-marketing observational study. In this study, patients with metastatic renal cell carcinoma from centers in 12 NUTS regions of Turkey will be included,

who meet the inclusion criteria. Since this is a non-interventional observational study, there is no specific follow-up protocol.

Presuming that there are 1800 patients with metastatic renal carcinoma in Turkey, the minimum sample size was calculated as 152.

There will be a total of 25 centers in various cities of Turkey.

The centers will consist of medical oncology clinics.

In this study, the patient follow-up period is 12 months. Each patient will be followed up to 5 times; the data will be collected at baseline, the 3rd, 6th, 9th and 12th months according to the routine practice. Additionally, every patient will be followed-up once for survival follow-up in order to assess the overall survival before the site close out visit. Survival follow-up will be performed via telephone visit or site visit if exist.

Because of the observational nature of the study, there is no predefined treatment protocol. The participating physician will continue to treat the patients at his/her own discretion. Frequency of visits will be continued per physician's preference.

The patients will be asked to fill in the quality of life questionnaire (FKSI-15, EQ5D-3L, FKSI-DRS) on each visit.

The assessment of the side effects will be based on the "Common Terminology Criteria for Adverse Events". The CTCAE V.4.03 will be used.

Outcome Measures are overall objective response rate (ORR) [Time frame: from enrollment to objective response], progression-free survival (PFS) [Time frame: from enrollment to disease progression or death, whichever occurs first], overall survival (OS) [Time frame: from enrollment to death or the end of the study duration] and probability of patient survival at 1 year [Time frame: from enrollment to 1 year]

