PFS, OS and ORR evaluation during 3rd, 6th, 9th and 12th months performed according to RECIST version 1.1, additionally, every patient will be followed-up once for survival follow-up in order to assess the overall survival before the site close out visit. Survival follow-up will be performed via telephone visit or site visit if exist.

ORR: The best overall response is the best response recorded from the start of the study treatment until the end of treatment taking into account any requirement for confirmation. The patient's best overall response assignment will depend on the findings of both target and non-target disease and will also take into consideration the appearance of new lesions. Furthermore, depending on the nature of the study and the protocol requirements, it may also require confirmatory measurement.

PFS: The length of time during and after the treatment of a disease, that a patient lives with the disease but it does not get worse. In a clinical trial, measuring the progression-free survival is one way to see how well a new treatment works.

OS: 1 year Overall Survival (OS), defined as the time from the start of 3rd line treatment until death or 1 year due to any cause (measured at the end of follow-up).

Data Sources

The source of the data will be the electronic or the written patient records of the participating centers. The patient's data can be accessed through a patient file. In the centers, both systems can be used in conjunction. The data can be accessed using both systems.

Sample Size

This is a multi-center, national, non-interventional/observational study. In this study, patients with metastatic renal cell carcinoma who meet the inclusion criteria will be included from centers in 12 NUTS regions of Turkey. Since this is a non-interventional observational study, there is no specific follow-up protocol. In this study, approximately 152 patients will be evaluated.

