Adverse events will be summarized using the CTCAE.4.03 coding system. Event rates for single adverse events will be calculated based on the total number of patients valid for safety. Adverse events will be categorized according to relation, seriousness, CTCAE grade (version 4.03), and discontinuation of therapy, action taken and outcome. Special attention will be paid to serious adverse events and unexpected or unlisted ADRs.

Category counts and frequencies (percentages) will be calculated for overall tolerability.

Since the enrollment is after the initiation of the treatment, some information will be collected and analyzed retrospectively.

The best overall response is the best response recorded from the start of the study treatment until the end of treatment taking into account any requirement for confirmation.

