8.2.1. Inclusion criteria

Patients must meet all of the following inclusion criteria to be eligible for inclusion in the study:

- Histologically confirmed metastatic renal cell cancer patients who have already been using targeted therapies for up to 1 months as 3rd line treatment
- Patients 18 years and older than 18 years
- Evidence of a personally signed and dated informed consent document indicating that the patient (or a legal representative) has been informed of all pertinent aspects of the study.

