8.3. Variables

The outcome variables for the objective(s) are time to treatment failure (from start of treatment to progression or permanent discontinuation), overall survival (from start of treatment to the date of last follow up or death), therapeutic response to therapy based on response evaluation criteria in solid tumors (RECIST version 1.1), and safety (type, incidence, severity of adverse events graded by the National Cancer Institute [NCI] CTCAE V.4.03)

Variable	Role	Data source(s)	Operational definition
Age, gender, height, weight, blood pressure, socio-demographic characteristics	Baseline characteristic	Medical Records	
Concomitant diseases	Baseline Characteristic	Medical Records	
Medication	Baseline Characteristic	Medical Records	
Histopathological findings	Baseline Characteristic	Medical Records / Pathology Reports	
Surgical Operations	Baseline Characteristic	Medical Records	
The cytokine (interferon alpha) usage in the first-line treatment, TKI usage in the 2 nd line treatment and the dosage and the duration of the treatment	Baseline Characteristic	Medical Records	
Metastatic features	Baseline Characteristic	Medical Records	
MSKCC risk factors	Baseline Characteristic Follow-up Characteristic	Medical Records	
3 rd line treatment	Baseline Characteristic Follow-up Characteristic	Medical Records	

	Close-out Characteristic		
The performance score before the second and third-line treatment		Medical Records	
The quality of life questionnaire (FKSI-15, EQ5D-3L, FKSI-DRS) on each visit	Baseline Characteristic Follow-up Characteristic Close –out Characteristic	Patient interview	
Blood pressure		Patient diary	
Other treatment during follow-up, if any, the dose and the duration	Follow-up Characteristic	Medical Records	
Treatment of the side effects, interruption of the treatment, dose reduction, dose-elevation	Baseline Characteristic Follow-up Characteristic	Medical Records	
Duration of PFS, OS and ORR	Follow-up Characteristic Close-out Characteristic	Medical Records	

Schedule Procedure	Initial visit	Follow-up 3.month	Follow-up 6.month	Follow-up 9.month	Follow-up 12.month	Survival Follow-up
Demographic data	X					
Histopathological Findigs	X					
Medical history	X					
Previous therapy of mRCC	X					
MSKCC Risk Factors	X	X	X	X	X	
Surgical Operations	X					
Metastases Information	X					
FKSI-15, EQ5D-3L, FKSI-DRS Questionnaire	X	X	X	X	X	
Evaluation of PFS,OS and ORR		X	X	X	X	
Concomitant medication	X	X	X	X	X	
Visit date	X	X	X	X	X	

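### Overall survival and 1-year survival start at enrolment in section 8.1 but at treatment start in the abstract and section 8.3, up to 1 month earlier, and no delayed-entry rule is given

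*Combined protocol and SAP*

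**What the plan says.** The outcome list in section 8.1 puts its time-to-event measures on an enrolment clock: "overall survival (OS) [Time frame: from enrollment to death or the end of the study duration", "probability of patient survival at 1 year [Time frame: from enrollment to 1 year" and "progression-free survival (PFS) [Time frame: from enrollment to disease progression or death, whichever occurs first".

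Two other places use treatment start. The Variables part of the abstract has 1-year OS "defined as the time from the start of 3rd line treatment until death or 1 year due to any cause". Section 8.3 has "overall survival (from start of treatment to the date of last follow up or death" and, for time to treatment failure, "time to treatment failure (from start of treatment to progression or permanent discontinuation".

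These are different dates by design. Section 8.2.1 admits patients "who have already been using targeted therapies for up to 1 months as 3rd line treatment", and the Data Analysis part of the abstract adds: "Since the enrollment is after the initiation of the treatment, some information will be collected and analyzed retrospectively".

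Kaplan-Meier summaries are planned (abstract and section 8.7) for PFS, TTP and time to treatment failure. OS is not in that list. Neither section 8.6 nor section 8.7 mentions delayed entry, left truncation or a landmark.

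**The concern.** One year from enrolment is 12 to 13 months from first dose. Two analysts, one following section 8.1 and the other the abstract or section 8.3, would report different 1-year OS from the same data. Nothing in the documents says which section prevails, so the choice could be made after the results are seen.

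The treatment-start clock has a further problem. A patient who dies before enrolment cannot enter the study. If ordinary Kaplan-Meier is run from first dose, every enrolled patient contributes an interval before enrolment in which death was impossible by selection. The curve is then too high. Time to treatment failure has the same exposure, as far as early progression or discontinuation keeps a patient out.

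**Working it through.** **1. The origins side by side**

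| Measure | Abstract | Section 8.1 | Section 8.3 |
|---|---|---|---|
| OS | – | enrolment | start of treatment |
| 1-year OS | start of 3rd line treatment | enrolment | – |
| PFS | no start date given | enrolment | – |
| Time to treatment failure | – | – | start of treatment |

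Section 8.3 does not name the line of treatment; it is read here as 3rd line. For 1-year survival only the origin conflicts. For full OS the end also varies in wording (end of study duration in 8.1, last follow-up in 8.3). The two ends may coincide at the survival contact, but they are not written as one censoring rule.

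**2. The plan's own figure**

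Sections 3 and 8.5 give N = 152 from a 7.6 confidence interval, 95% confidence and a population of 1800. Taking 7.6 as a half-width in percentage points and assuming a proportion of 0.5:

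- n0 = 1.96² × 0.25 / 0.076² = 166.27
- with finite-population correction: 166.27 / (1 + 165.27/1800) = 152.3

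The stated 152 reproduces. No time origin enters it.

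**3. Size for 1-year OS**

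Assumptions, since the documents give no rates: Weibull survival S(t) with median 10, 12, 15 or 18 months and shape 0.8, 1.0 or 1.3. Entry time E is uniform over 0-1 month or, as an extreme, 1 month for everyone. A patient enrols only if alive at E.

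- True value from first dose: S(12)
- Ordinary Kaplan-Meier from first dose: S(12) / E[S(E)]
- Enrolment clock: E[S(12+E)] / E[S(E)]

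Example, exponential with median 12 and uniform entry: S(12) = 50.0% and E[S(E)] = 0.9717. The first-dose clock gives 50.0/0.9717 = 51.5%. The enrolment clock gives 50.0%, because a constant hazard has no memory.

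| Over all medians and shapes (percentage points) | Uniform entry | All at 1 month |
|---|---|---|
| Ordinary first-dose clock minus truth | 0.5 to 2.8 | 1.1 to 5.2 |
| Ordinary first-dose clock minus enrolment clock | 1.0 to 2.0 | 2.1 to 4.0 |
| Enrolment clock minus truth | -1.3 to +1.6 | -2.5 to +2.6 |

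For scale, the standard error at n = 152 and 50% survival is √(0.25/152) = 4.1 points.

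**4. Size for time to treatment failure**

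Assume a true median of 4 months, the same shapes and uniform entry. Let s be the share of the early failure hazard that prevents enrolment. Solve S(t) / E[S(E)^s] = 0.5 and subtract 4:

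- s = 1: median too long by 0.2-0.9 months
- s = 0.5: 0.1-0.5 months
- s = 0.25: 0.05-0.2 months

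Scheduled evaluation begins at month 3, so s is probably below 1.

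**5. Would a delayed-entry analysis do better?**

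Simulation with n = 152, 3,000 runs per scenario, medians 10, 12 and 18 and the three shapes. Root mean squared error against true first-dose 1-year OS, in points:

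| Method | Uniform entry | Late entry, Beta(3,1) |
|---|---|---|
| Enrolment clock | 3.8-4.4 | 3.9-4.6 |
| Ordinary first-dose clock | 3.9-5.0 | 3.9-5.8 |
| Left-truncated first-dose clock | 4.0-5.2 | 4.8-6.9 |

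Left truncation removes the bias but gives back at least as much in variance at this sample size.

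**The case against.** The brackets in section 8.1 can be read as observation windows and not as definitions: one is attached to the response rate, which is not a duration. The abstract and section 8.3 both use treatment start, so amending section 8.1 alone would reconcile the text. That is a fair route. It does not remove the conflict as written, and it leaves the delayed-entry question open.

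The gap may also be small. The inclusion criterion allows a lag near zero, and the safety reporting period in section 10 provides for consent by first dose. Entry of every patient at 1 month has no support in the documents, so the right-hand column of the OS table is only a bound. The differences sit inside sampling error, OS is secondary, time to treatment failure is not a listed objective, and no hypothesis is tested. All of this stands, and it limits the weight of the point. Unlike sampling error, however, the bias does not shrink with more patients.

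The simulation shows that left truncation brings no gain in total error at n = 152. That stands too, so it should not be presented as the only acceptable method.

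A reader might infer that time to treatment failure will exceed PFS by the lag before enrolment. The documents do not support this. Time to treatment failure also ends at permanent discontinuation, and PFS also ends at death. A patient enrolled at 0.5 month who stops for toxicity at month 2 and progresses at month 5 has a time to treatment failure of 2.0 months and a PFS of 4.5. Only the origins can be said to differ.

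**Conclusion.** The origin of OS and 1-year OS is contradictory as written, and nothing in the documents resolves it. With uniform entry over 0-1 month, the two readings differ by about 1-2 points in 1-year OS. Ordinary Kaplan-Meier on the treatment-start clock would be about 0.5-2.8 points too high. Both figures rest on the assumed medians of 10-18 months and Weibull shapes of 0.8-1.3. The OS bias is also conditional on the estimator, because the plan names none for OS.

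For time to treatment failure Kaplan-Meier is planned, so the exposure is direct, but its size depends on how many early failures prevent enrolment. Its origin also differs from the only one stated for PFS.

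The point should be fixed, but it is modest. A reader might extend it to the sample size or to primary PFS. N does not depend on the time origin. PFS has a single stated origin, and on that clock the interval before enrolment is not counted as event-free time.

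**What to change.** State one origin for OS and 1-year OS in the abstract, section 8.1 and section 8.3, and state the origin of time to treatment failure consistently with PFS. Either choice is defensible.

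- **Enrolment.** Describe results as conditional on reaching enrolment, report time since first dose at enrolment, and state how a progression or discontinuation before enrolment is handled, since it would otherwise give a zero or negative duration. The cost is that the estimate describes only patients who reached enrolment. With uniform entry it differs from true first-dose 1-year OS by -1.3 to +1.6 points, and by 0 under constant hazard.
- **Treatment start.** Enter each patient into the risk set at the enrolment date (left-truncated Kaplan-Meier). This removes the bias but costs precision: a standard deviation of 4.0-5.2 points for 1-year OS with uniform entry, against 3.8-4.1 for the enrolment clock. It also cannot recover the first month if nearly all patients enrol at 1 month. Alternatively, report the ordinary estimate with the bias stated and the enrolment-origin result as a sensitivity analysis.

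In either case, add OS to the Kaplan-Meier list in the abstract and section 8.7, censor at last known alive including the survival contact, and read 1-year OS from the curve at 12 months. As a side correction, align the response window in section 8.1 with the best-response definition, which runs from start of treatment.

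These are wording changes before database lock. They add no visits and leave N unchanged. The first-dose date is already needed to apply the 1-month criterion.

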8.2. Setting

Metastatic renal cell carcinoma patients who progressed after a TKI therapy following a cytokine (interferon alpha) treatment will be enrolled to the study. The study enrollment period is 12 months And the follow-up period of a patient is 12 months.The study period is 36 months.

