8.8. Quality control

Data will be captured with e-CRF. Missing data should be completed or commented upon by the physician. After data checked, missing or implausible data will be queried. A check for multiple documented patients will be done. The data will be verified by an error analysis. Finally source data verification will be conducted in all of patients, 100% SDV will be performed. All investigators will be sufficiently trained for participation in the study.

To enable evaluations and/or audits from regulatory authorities or Pfizer, the investigator agrees to keep records, including the identity of all participating patients (sufficient information to link records, e.g., CRFs and hospital records), all original signed informed consent forms, copies of all CRFs, serious adverse event forms, source documents, and detailed records of treatment disposition, and adequate documentation of relevant correspondence (e.g., letters, meeting minutes, telephone calls reports). The records should be retained by the investigator according to local regulations, or as specified in the Clinical Study Agreement, whichever is longer.

If the investigator becomes unable for any reason to continue to retain study records for the required period (e.g., retirement, relocation), Pfizer should be prospectively notified.

The study records must be transferred to a designee acceptable to Pfizer, such as another investigator, another institution, or to an independent third party arranged by Pfizer. The investigator must obtain Pfizer's written permission before disposing of any records, even if retention requirements have been met.

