9.4. Ethical Conduct of the Study

The study will be conducted in accordance with legal and regulatory requirements, as well as with scientific purpose, value and rigor and follow generally accepted research practices described in Guidelines for Good Pharmacoepidemiology Practices (GPP) issued by the International Society for Pharmacoepidemiology (ISPE), Good Epidemiological Practice (GEP) guidelines issued by the International Epidemiological Association (IEA).

This is a non-interventional study where the 3rd line targeted treatment are prescribed in the usual manner in accordance with the terms of the marketing authorization. There is no assignment of a patient to a particular therapeutic strategy, the treatment decision falls within current practice and the prescription of the medicines is clearly separated from the decision to include the patient in the study. No additional diagnostic or monitoring process is required for participation or during the study. Epidemiological methods shall be used for the analysis of the collected data.

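### Patients are enrolled up to a month into 3rd-line therapy with no consecutive-enrolment rule and no log of starters who were not enrolled, so early failures can go missing unmeasured

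*Combined protocol and SAP*

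**What the plan says.** - **Entry follows treatment start.** Section 8.2.1 admits patients "who have already been using targeted therapies for up to 1 months as 3rd line treatment". The abstract acknowledges this: "Since the enrollment is after the initiation of the treatment, some information will be collected and analyzed retrospectively". The only consequence it draws concerns data collection, not who ends up in the sample.
- **Eligibility is described, sampling is not.** Section 8.2 reads "Metastatic renal cell carcinoma patients who progressed after a TKI therapy following a cytokine (interferon alpha) treatment will be enrolled to the study", and section 8.1 is similar. Neither says whether all eligible patients, consecutive patients or some sample of them are to be enrolled.
- **Inclusion is a decision of its own.** Section 9.4 states that "the prescription of the medicines is clearly separated from the decision to include the patient in the study". It does not say who decides on inclusion or by what rule.
- **Records cover enrolled patients only.** Under section 8.8, "the investigator agrees to keep records, including the identity of all participating patients". No screening or eligibility log is mentioned anywhere.
- **Limitations are not discussed.** The table of contents lists a section 8.9 on limitations of the research methods. In the body, 8.9 is Other aspects, marked not applicable.

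**The concern.** Quality of life, ORR and median PFS are the primary objectives, and all three are estimated in the patients who were enrolled. The efficacy set in section 8.7 is called intent-to-treat and is built on having had at least one 3rd-line dose, but a starter who is never enrolled cannot be in it.

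Patients can be lost by two routes. First, someone who dies or permanently stops before being approached cannot readily meet the entry criterion. Second, someone still on treatment but doing badly may simply not be invited, because nothing requires an invitation. Delayed-entry methods can address the first route for outcomes timed from treatment start. They cannot repair the second, because they assume that entry is unrelated to prognosis among those still at risk.

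Without a log, neither route can be measured afterwards. The study's stated purpose is to describe 3rd-line treatment in Turkey, so this bears directly on what the results can be said to represent.

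**Working it through.** **1. The plan's own figure.** Section 8.5 gives 152 from a population of 1800, a precision of 7.6 (read as ±7.6 percentage points) and 95% confidence. A proportion of 0.5 is assumed here; the protocol does not state it.

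- n0 = 1.96² × 0.25 / 0.076² = 166.3
- With finite-population correction: n = 166.3 / (1 + 165.3/1800) = 152.3

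This matches 152. The formula presumes a random sample of the 1800, and no rule in sections 8.1, 8.2 or 8.2.1 delivers one.

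**2. Effect of losing early failures, by either route.** The documents give no early-failure rates, so all rates below are assumptions: 5–15% of starters do badly in month 1, none of them responds or survives one year, and half to all of them are not enrolled.

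Observed = true / (1 − share doing badly × share of those not enrolled)

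| Outcome | True | Lowest (5% × half) | Highest (15% × all) |
|---|---|---|---|
| 1-year OS from treatment start | 50% | 0.50/0.975 = 51.3% | 0.50/0.85 = 58.8% |
| ORR | 10% | 0.10/0.975 = 10.3% | 0.10/0.85 = 11.8% |

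The shift is 1.3 to 8.8 points for OS and 0.3 to 1.8 points for ORR. The OS shift exceeds 7.6 points only if more than 1 − 0.50/0.576 = 13% of all starters are missing.

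**3. Separating the routes, using median PFS.** Assume exponential PFS with a true median of 4 months.

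- *Entry rule alone, clock from treatment start:* the apparent median is about 4.5 months if entry is uniform over the first month, and 5 months if everyone enters at 1 month.
- *Entry rule alone, clock from enrolment:* the median stays at 4.0. Section 8.1 uses this clock: "progression-free survival (PFS) [Time frame: from enrollment to disease progression or death, whichever occurs first".
- *Selective omission as well, clock from enrolment:* leave out a fraction f of those who would fail within 2 months of entry. With λ = ln 2/4 = 0.1733, the share failing within 2 months is 1 − exp(−2λ) = 0.293. The apparent median m solves exp(−λm) = 0.5 × (1 − 0.293f). For f = 0.25, m = 4.4 months; for f = 0.5, m = 4.9 months.

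The same selective omission moves a true median of 3 months to 3.4–3.9, and one of 6 months to 6.5–6.9. Choosing the enrolment clock therefore removes the first route under a constant hazard, but not the second.

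**4. Quality of life.** The documents give no score distribution, so no figure can be put on this outcome.

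**The case against.** A reader might infer that physicians pick the patients they expect to do well. The documents do not support that. Sections 8.1 and 8.2 say that patients meeting the criteria will be included, and section 9.4 only separates prescribing from inclusion. What the text shows is an unspecified rule, not a known practice.

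A reader might also infer that the physician already knows who is failing. One month is a maximum, some patients may enter within days, and the first scheduled response assessment is at month 3. Death, clinical decline or toxicity may be visible before enrolment, but no study response assessment is.

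Nor is upward bias certain for every outcome. With PFS timed from enrolment and a constant hazard, the entry rule alone causes none. Section 8.3 and the abstract time OS from treatment start, while section 8.1 times it from enrolment; that conflict needs its own resolution.

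The strongest argument on size is that the ORR shift is small against ±7.6 points, and that the OS shift passes that mark only near the extreme of the assumed range, for a secondary outcome. The study is also described as explorative, with no hypothesis to test. All of this stands, and it limits how strongly the point can be put. It does not remove the gap: a descriptive study depends on knowing whom it describes, and this plan gathers nothing to show that.

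**Conclusion.** The concern holds in a limited form. Enrolment follows treatment start by up to a month, no rule requires all or consecutive eligible patients to be invited, and nothing is recorded about starters who are not enrolled. Outcome-related selection is therefore permitted and cannot be measured later. Its direction is probably favourable to the results. That rests on the reasoning that early deaths, stops and poorly tolerating patients are the ones most easily lost, not on any statement in the protocol.

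The illustrated ranges in OS and ORR combine loss through the entry rule with loss by choice, and rest entirely on assumed rates. They show what could happen, not an estimate for this study. The point is a worthwhile and inexpensive design improvement; it does not invalidate the study.

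**What to change.** Add to sections 8.2 and 8.2.1, for example:

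> From this version on, each centre invites all consecutive eligible patients at the first visit after the first 3rd-line dose. Each centre keeps an anonymous log of every patient starting 3rd-line therapy: drug, start date, enrolled or not, and the reason if not (ineligible, died, stopped, declined, missed).

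In the analysis and report:

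- Show the patient flow from starters to enrolled.
- State selection as a limitation, in the section that the table of contents already announces.
- Add a sensitivity bound. Non-enrolled early deaths count as non-responders and PFS events. Early stops count as non-responders and treatment-failure events, but not as PFS events, in line with the definitions in sections 8.1 and 8.3. Eligible patients who declined or were missed count as non-responders in the worst case.
- Complete the log for earlier starters only where ethics approval allows, since these patients have not consented.

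**Cost.** "There will be a total of 25 centers in various cities of Turkey", so 152/25 is about 6 enrolled patients per centre. The extra work is a short log per centre and one flow table. N does not change, and no diagnostic or monitoring procedure is added. The log may need ethics review.

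Coverage will be incomplete. Version 2.1 is dated March 2016, while the first visit was planned for May 2015. Under the milestones in section 5, about nine months of enrolment remained, to December 2016. Twelve months of enrolment from May 2015, as section 8.2 would imply, leaves only about two.
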